4.2.2 Secondary Efficacy

The secondary efficacy objective will be evaluated at 5 minutes in a manner similar to the primary efficacy analysis. The secondary hypothesis for this clinical investigation is that the proportion of subjects achieving hemostasis of the treated bleeding site at 5 minutes in the PerClot group is non-inferior to the proportion of subjects achieving hemostasis of the treated bleeding site at each evaluation time point in the control group.

$$H_0: P_{t,PerClot} < P_{t,Control} - \delta$$
$$H_a: P_{t,PerClot} \geq P_{t,Control} - \delta$$

where $P_{PerClot}$ is the proportion of PerClot subjects achieving hemostasis of the treated bleeding site at time point t , $P_{t,Control}$ is the proportion of control subjects achieving hemostasis of the treated bleeding site at time point t , and δ is the non-inferiority margin, with $\delta = 0.10$.

In other words, the null hypotheses are that the proportion of PerClot subjects achieving hemostasis of the treated bleeding site at each evaluation time point will be inferior to the proportion of control subjects achieving hemostasis of the treated bleeding site at each evaluation time point. The alternative hypotheses are that the proportion of PerClot subjects achieving hemostasis of the treated bleeding site at each evaluation time point will be equal to or greater than, or not inferior to, the proportion of control subjects achieving hemostasis of the treated bleeding site at each evaluation time point. Each null hypothesis will be rejected in favor of the corresponding alternative hypothesis if the upper bound of the 97.5% one-sided confidence interval for the difference in treatment proportions ($P_{t,Control} - P_{t,PerClot}$) is less than 0.10.

4.2.3 Trial Success Criteria

Trial success will be the rejection of the primary efficacy null hypothesis, with the upper bound of the 97.5% one-sided confidence interval for the difference in proportions of subjects achieving hemostasis at 7 minutes between treatment groups ($P_{Control} - P_{PerClot}$) being less than 0.10, in the As Treated population.

4.3 Analysis Populations

Analysis populations are defined as follows:

- The Intent-to-Treat (ITT) population includes all randomized subjects, regardless of treatment received;
- The As Treated (AT) population includes all subjects who were randomized and treated with either PerClot or Arista, with subjects assigned to the treatment group for the treatment received (even if this differs from randomization assignment); and

- The Per Protocol (PP) population includes all subjects who were randomized and treated with either PerClot or Arista, and had no major protocol deviations, where major protocol deviations are defined as:
 - Failure to meet any preoperative inclusion/exclusion criteria;
 - Failure to meet any intraoperative inclusion/exclusion criteria; or
 - Any informed consent violation.

All efficacy analyses and summary statistics will be performed on the ITT, AT, and PP populations. Safety analyses will be performed on the ITT population.

Trial success will be evaluated on the AT population. Effectiveness analyses of the ITT and PP populations will be supportive of the AT analysis. Any clinically significant differences in effectiveness results between the analysis populations will be examined relative to protocol deviations and discussed.

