A sample size of 154 subjects in each group will provide $>$ approximately 80% power to reject the hypothesis of the inferiority of PerClot to the control by a 10% margin, using a one-sided 97.5% confidence interval. As the primary endpoint data is collected intraoperatively, no adjustment is made for attrition; however, the sample size was increased to account for the possibility of up to 5% loss within either group due to technical failures (i.e., contraindications, misdiagnosis, or intraoperative death prior to treatment, etc.), or subjects not treated according to randomization assignment, resulting in a sample size of 162 per arm to ensure $>$ 80% power in the overall sample including all three therapeutic areas. Thus, a total of 324 subjects will be enrolled across the three therapeutic areas. It is expected that there will be approximately equal numbers randomized within each of the three therapeutic areas, with an approximate 108 subjects in each therapeutic cohort.

A non-inferiority margin of 10% is consistent with the margins used in other controlled clinical trials involving hemostatic agents.^{24, 25} A non-inferiority margin $\delta = 0.10$ was chosen for this study because excluding a 10% difference between the treatments would be supportive of non-inferior performance of PerClot compared to the control.

6.6.6 *Blinded Sample Size Re-estimation*

In order to protect against lower than planned power due to misspecification of the assumed success rates, blinded sample size re-estimation will be performed.²⁶ The initial sample size

calculation will be repeated based on the observed pooled efficacy rate (i.e. the proportion of all subjects, regardless of randomization assignment, with 7 minute hemostatic success) rather than the initially assumed rate of 90%.

The re-estimation will be performed using the efficacy results of the first 20% and 50% of the minimum planned enrollment of 324(i.e. 64 and 162 subjects) pooled across randomized arm. The re-estimated sample size after 20% enrollment will provide an initial re-calibration of the sample size. The re-estimated sample size after 50% enrollment will determine the final sample size, which may be lower or higher than the re-estimated sample size after 20% enrollment.

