4.2.1.1 Sample Size Justification

The sample size was calculated based on the following assumptions:

- One-sided alpha = 0.025;
- Minimum 80% power;
- Non-inferiority margin $\delta = 0.10$;
- Expected 7 minute hemostatic success rate in the PerClot group is 90%; and
- Expected 7 minute hemostatic success rate in the control group is 90%.
- Randomization allocation of 1:1

A sample size of 154 subjects in each group will provide approximately 80% power to reject the hypothesis of the inferiority of PerClot to the composite control by a 10% margin, using a one-sided 97.5% confidence interval (see Appendix A). As the primary endpoint data is collected intraoperatively, no adjustment is made for attrition; however, the sample size was increased to account for the possibility of up to 5% loss within either group due to technical failures (i.e., contraindications, misdiagnosis, or intraoperative death prior to treatment, etc.), and subjects not treated according to randomization assignment, resulting in a sample size of 162 per arm to ensure >80% power. Thus, a total of 324 subjects is the planned sample size to enroll, assuming an efficacy rate of 90%.

A non-inferiority margin of 10% is consistent with the margins used in other controlled clinical trials involving hemostatic agents.^{2, 3} A non-inferiority margin $\delta = 0.10$ was chosen for this study because excluding a 10% difference between the treatments would be supportive of non-inferior performance of PerClot compared to the control.

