4.4.4 Safety Analyses

Safety data will be summarized by incidence of each adverse event type along with 95% exact confidence intervals. Adverse event rates will be reported as the proportion of subjects who experience an event and the total number of each event type occurring.

Adverse events will be summarized by relatedness, seriousness, and severity. The comparison of safety between treatment arms will be based on Fisher's exact tests for the proportion of subjects with serious device-related adverse events, unanticipated adverse device effects, and frequent adverse events ($\geq 5\%$ overall incidence) in the two treatment groups.

The other following safety endpoints will also be summarized using descriptive statistics:

- Total operative time;
- Hemostasis at 5 to 7 minutes;
- Hemostasis maintenance;
- Total intraoperative estimated blood loss;
- Alternative means required to achieve hemostasis (where applicable);
- Units of blood transfused intraoperatively and postoperatively (where applicable);
- Incidence of reoperation;
- Total hospitalization time;
- Incidence of procedure complications;
- Incidence of adverse events through final follow-up, including, but not limited to:
 - Adhesions or fibrosis;
 - Anaphylaxis;
 - Blockage of the bladder or ureteral lumen;
 - Blockage of the bypass system;
 - Cancer recurrence and/or progression;
 - Compromised attachment of prosthetic devices to bone or tissue;
 - Death;
 - Embolism;
 - Failure of deep or superficial wound healing;
 - Failure to obtain hemostasis;
 - Fever;
 - Hemorrhage;
 - Infection;
 - Peri-operative hyperglycemia;
 - Exacerbation of surgical procedure-associated adverse events;
 - Swelling and compression of pressure-sensitive tissues and structures;
 - Thromboembolism;
 - Thrombosis; and
 - Toxicity.

Safety analyses are descriptive in nature. There are no formal hypothesis tests associated with these outcomes. All safety analyses will be performed on the ITT population.

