4.5 Subgroup Analysis

Analyses will be conducted to determine the consistency of study results across the following subgroups: gender, race, and bleeding severity score. These analyses will be descriptive in nature, and as such there are no formal hypothesis tests. There are no labeling claims being sought out for these subgroups analyses.

Subgroup analyses will be performed on the primary efficacy measure (proportion achieving hemostasis at 7 minutes), secondary efficacy measure (proportion achieving hemostasis at 5 minutes), and safety measures (proportion with device related events and serious adverse events). For efficacy measures, analyses will be performed on the AT population. Safety subgroup analyses will be based on the ITT population.

For each endpoint measure the proportion of subjects will be reported by subgroup. The difference in proportions and its associated 95% confidence interval will be reported by subgroup. To test for a differential treatment effect across subgroups a logistic regression model will be fit, testing for the interaction of treatment group by subgroup. In the case that poolability across a subgroup is questionable, as indicated by statistical significance of the interaction effect at $\alpha \leq 0.05$, the estimated treatment difference and 95% confidence interval from the subgroup adjusted logistic regression model will be reported.

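### Adverse events are tabulated only on the ITT set, never by device received, and Per Protocol keeps subjects given the wrong device

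*SAP*

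**What the plan says.** SAP 4.3 defines three sets. ITT is every randomised subject whatever was received. As Treated is every randomised and treated subject, "with subjects assigned to the treatment group for the treatment received (even if this differs from randomization assignment"). Per Protocol "includes all subjects who were randomized and treated with either PerClot or Arista, and had no major protocol deviations". The major deviations are a closed list: preoperative eligibility failure, intraoperative eligibility failure and consent violation. Protocol 6.6.9 uses the same definitions.

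The sets are used as follows:

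- **Trial success** (SAP 4.2.3), **efficacy subgroups** (4.5) and **poolability** (4.7): As Treated.
- **Supportive efficacy**: ITT and Per Protocol.
- **Safety**: ITT only. SAP 4.3 has "Safety analyses will be performed on the ITT population", SAP 4.4.4 has "All safety analyses will be performed on the ITT population", and SAP 4.5 has "Safety subgroup analyses will be based on the ITT population".

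The one rule for comparing populations is limited to efficacy: "Any clinically significant differences in effectiveness results between the analysis populations will be examined relative to protocol deviations and discussed".

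Both documents expect some wrong-device subjects. The allowance of up to 5% covers technical failures together with such subjects (protocol 6.6.5: "or subjects not treated according to randomization assignment, resulting in a sample size of 162 per arm"; SAP 4.2.1.1: "and subjects not treated according to randomization assignment, resulting in a sample size of 162 per arm"). Protocol 6.4.3.4 has both products brought into the operating room. Protocol 6.2.3 permits only the randomised product on the qualifying site.

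**The concern.** A safety table in a comparison of two devices is read as a statement about the devices. The investigator judges causality against the hemostatic device (protocol 9.2 and the Adverse Event form), and SAP 4.4.4 compares serious device-related events and unanticipated device effects between arms by Fisher's exact test. If a subject randomised to Arista receives PerClot and has a PerClot-related event, the ITT table lists it under Arista. On average this pulls the arms together. For a rare serious event it can change how the table reads.

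The plan treats device received as the right grouping for deciding whether PerClot works, yet offers no such grouping for harm.

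Per Protocol is one of two supportive checks on the As Treated result. It admits anyone treated with either product and does not exclude those who got the wrong one, so it keeps subjects who breached the treatment assignment. The plan also does not say in which arm Per Protocol counts them.

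**Working it through.** **The plan's own figure.** With the Farrington-Manning score test, one-sided alpha 0.025, margin 0.10 and 90% success in both arms, the normal-approximation formula gives 154.4 per arm and power 0.79885 at 154. This matches SAP Appendix A. The 5% allowance gives 154 × 1.05 = 161.7, so 162 per arm. No sample-size error is involved. 5% of 162 is 8.1, about 8 subjects per arm.

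**Inputs not in the documents.** No wrong-device rate or adverse-event rate is given. Assumed here: a wrong-device share c of 1%, 3% or 5%, equal in both arms, and event rates by device received of 6% v 2%. The 5% is a planning allowance shared with technical failures, not a limit on switching.

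**Safety, average effect.** If an event depends on the device received, the ITT difference is (1 − 2c) times the true one.

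| c | ITT rates | ITT difference (points) | Shrinkage | Fisher power, 162 per arm |
|---|---|---|---|---|
| 0 | 6.00% v 2.00% | 4.00 | 0 | 34% |
| 1% | 5.96% v 2.04% | 3.92 | 2% | 32% |
| 3% | 5.88% v 2.12% | 3.76 | 6% | 30% |
| 5% | 5.80% v 2.20% | 3.60 | 10% | 27% |

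**Safety, at least one event under the wrong device.** With m wrong-device subjects per arm, the chance is 1 − 0.94^m × 0.98^m: 15% for m = 2, 34% for m = 5, 48% for m = 8.

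**Safety, a rare event.** Suppose 6 of 162 v 0 of 162 by device received: two-sided Fisher p = 0.030. If one of the six had been randomised to the other arm, and one event-free subject switched the opposite way so that denominators stay equal, ITT reads 5 v 1 and p = 0.214. This needs a switched subject to be among the six. The chance that at least one is: 1 − (156 × 155)/(162 × 161) = 7% with 2 wrong-device PerClot recipients, and 27% with 8. The 15% to 48% above belong to the 6% v 2% scenario and are not the probability of this example.

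**Per Protocol, if grouped as randomised and switching is unrelated to prognosis.** At the null boundary (80% v 90%), the PerClot arm's rate becomes 0.8(1 − c) + 0.9c and the control arm's 0.9(1 − c) + 0.8c. Exact enumeration of the score test with 162 per arm gives these chances of a false non-inferiority result:

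| c | False non-inferiority |
|---|---|
| 0 | 2.5% |
| 1% | 2.8% |
| 3% | 3.5% |
| 5% | 4.3% |

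With wrong-device subjects excluded (154 per arm) it returns to 2.5%. If Per Protocol is instead grouped by device received, this inflation does not arise.

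**Cost to Per Protocol power.** At 90% v 90%, exact power is 83.0% with 162 per arm and 80.8% with 154.

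**The case against.** The strongest reply is that this is a small matter of reporting. SAP 4.4.4 calls safety descriptive, and protocol and SAP agree with each other. On the assumed 6% v 2%, the loss is at most 0.4 percentage points, and Fisher power is only 34% even with no switching, so ITT is not the main limit on that comparison. Event-level safeguards exist: causality is judged per event, serious events and unanticipated device effects reach the sponsor within 24 hours, and the DSMB reviews accumulating data. Hemostasis at 5 and 7 minutes, also listed under safety, does get an As Treated analysis as efficacy. Per Protocol decides nothing, the deviation form has a randomisation category, and efficacy differences between populations must be examined against deviations.

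Much of this limits the size, and it is accepted. The 5% is not a ceiling on switching, and the one-swap example is unlikely when switching is rare. The calculations also hold 162 per arm, although re-estimation may raise the total to 536. The ITT definition states membership only; grouping by randomised arm is inferred from the name and from the contrast with As Treated.

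None of it supplies the missing table. Expedited reports and DSMB review do not correct the final safety summary. One could try to read the SAP 4.3 sentence putting all efficacy analyses and summary statistics on three populations as covering adverse events, but the next sentence and SAP 4.4.4 restrict safety to ITT. A descriptive table should still describe the device that was used.

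**Conclusion.** The concern holds on the text of both documents. Adverse events are confined to ITT, and the Per Protocol list omits receipt of the wrong device although protocol 6.2.3 forbids it. The effect is nil without switching. At 1% to 5% wrong-device use in both arms, the adverse-event contrast is diluted by 2% to 10%. A rare device-related event could also be listed under the wrong product. The Per Protocol inflation to between 2.8% and 4.3% depends on grouping as randomised, which the plan leaves open, and on prognosis-neutral switching. All these sizes rest on assumed rates. The As Treated success decision is untouched. This should be changed as a cheap improvement to reporting; it is not a flaw in the success test.

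**What to change.** **Safety** (SAP 4.3, 4.4.4, 4.5; protocol 6.6.9). State that adverse-event summaries, the Fisher comparisons and the safety subgroup analyses are presented for ITT by randomised arm and, alongside, for As Treated by device received. ITT should stay, because it keeps subjects randomised but never treated, including deaths before application (protocol 6.4.3.3).

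**Per Protocol** (SAP 4.3; protocol 6.6.9). Add receipt of a device other than the one randomised to the major deviations, and report the number by randomised arm. Assigned and received device then coincide in Per Protocol, so its grouping is no longer ambiguous.

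**Cost.** A few sentences, one more set of safety tables to be read with the first, and a slightly smaller Per Protocol set (power 83.0% to 80.8% if 8 per arm leave). Device received must already be derived for the success analysis, so no new data field is needed for this purpose. The derivation rule should be written down, though: the operative form places the device identifier in its enrollment and randomisation block, and Appendix N records it at step 12, before application at step 14. The success criterion does not change.

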6.4.3.4 Hemostat Application

The prescribed hemostatic agent will be applied according to the respective product Instructions for Use. Any device malfunctions will be recorded on the Device Malfunctions eCRF using FDA CDRH (Center for Devices and Radiological Health) Event Reporting nomenclature.²³ This will be a single-blinded trial. The subjects will be blinded as to the hemostatic treatment received. Unblinding will be permitted after a subject has completed his or her 6 week follow-up visit evaluation.

The anatomic site is defined as the approximate surface area of bleeding site, measured by multiplying the greatest perpendicular distances of the bleeding site. The anatomic application site is defined as the approximate surface area of the target application site, measured by adding one (1) centimeter to both greatest perpendicular distances of the bleeding site and multiplying the two values. The anatomic site and anatomic application site must meet all intraoperative eligibility criteria noted in Section 6.4.3.2. The anatomic site must not exceed 25cm². The anatomic application site must not exceed 47cm². Anatomic site and anatomic application site will be calculated and documented for the bleeding site on the Operative eCRF.

NOTE: The actual resection site may be larger than the anatomic site and/or anatomic application site (e.g., a liver resection site may be 5 inches by 4 inches, however you will only be allowed to evaluate investigational product on a 25cm² anatomic site).

The investigator will be allowed to use the entire contents of up to two 5 gram bellows of PerClot per investigational subject. Each box of PerClot supplied will contain five separate packages. Only two 5 gram bellows (packages) can be used per subject. Sites will be instructed to bring two packages of PerClot and two packages of the control product into the operating room on the day of the surgery. Application of investigational product will be addressed during investigator training. The exact amount of investigational product applied will be determined by weighing the device(s) before and after use.

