6.6.9 Analysis Populations

Analysis populations are defined as follows:

- The Intent-to-Treat (ITT) population includes all randomized subjects, regardless of treatment received;
- The As Treated population includes all subjects who were randomized and treated with either PerClot or Arista, with subjects assigned to the treatment group for the treatment received (even if this differs from randomization assignment); and
- The Per Protocol population includes all subjects who were randomized and treated with either PerClot or Arista, and had no major protocol deviations, where major protocol deviations are defined as:
 - Failure to meet any preoperative inclusion/exclusion criteria;
 - Failure to meet any intraoperative inclusion/exclusion criteria; or
 - Any informed consent violation.

All efficacy analyses and summary statistics will be performed on the ITT, As Treated, and Per Protocol populations. Safety analyses will be performed on the ITT population.

No subject will be removed from the study once randomization occurs. All randomized subjects with available outcome data will be included in the analysis, according to the defined analysis population.

Study success will be evaluated on the As Treated population. Effectiveness analyses of the ITT and Per Protocol populations will be supportive of the As Treated analysis. Any clinically significant differences in effectiveness results between the analysis populations will be examined relative to protocol deviations and discussed.

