4.2 Study Hypotheses

4.2.1 Primary Efficacy

The primary efficacy hypothesis for this clinical investigation is that the proportion of subjects achieving hemostasis of the treated bleeding site at 7 minutes in the PerClot group is non-inferior to the proportion of subjects achieving hemostasis at 7 minutes in the control group.

$$H_0: P_{\text{PerClot}} < P_{\text{Control}} - \delta$$

$$H_a: P_{\text{PerClot}} \geq P_{\text{Control}} - \delta$$

where P_{PerClot} is the proportion of PerClot subjects achieving hemostasis at 7 minutes, P_{Control} is the proportion of control subjects achieving hemostasis of the treated bleeding site at 7 minutes, and δ is the non-inferiority margin, with $\delta = 0.10$.

In other words, the null hypothesis is that the proportion of PerClot subjects achieving hemostasis of the treated bleeding site at 7 minutes will be inferior to the proportion of control subjects achieving hemostasis of the treated bleeding site at 7 minutes. The alternative hypothesis is that the proportion of PerClot subjects achieving hemostasis of the treated bleeding site at 7 minutes will be equal to or greater than, or not inferior to, the proportion of control subjects achieving hemostasis of the treated bleeding site at 7 minutes. The null hypothesis will be rejected in favor of the alternative hypothesis if the upper bound of the 97.5% one-sided confidence interval for the difference in treatment proportions ($P_{\text{Control}} - P_{\text{PerClot}}$) is less than 0.10.

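### Trial success rests on the As Treated population alone; no as-randomized result has to agree, and the per-protocol set keeps subjects who received the wrong device

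*SAP*

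**What the plan says.** SAP 4.2.3 and Protocol 6.6.7 define trial success as the upper 97.5% one-sided bound for control minus PerClot falling below 0.10 in the As Treated population. SAP 4.3 repeats that "Trial success will be evaluated on the AT population", and Protocol 6.6.9 that "Study success will be evaluated on the As Treated population". As Treated comprises subjects randomized and treated with either device, "with subjects assigned to the treatment group for the treatment received (even if this differs from randomization assignment".

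ITT and PP are analysed on the same endpoint but are labelled supportive. If the sets differ to a clinically significant degree, the difference is to be examined against protocol deviations and discussed; no rule makes agreement a condition of success. The major deviations that remove a subject from PP are eligibility failures and informed consent violations. Receiving the wrong device is not among them.

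On conduct, only the subject is blinded (SAP 3, Protocol 6.6.8). Assignment is by envelope after intraoperative eligibility is confirmed (Protocol 6.4.3.3). "Sites will be instructed to bring two packages of PerClot and two packages of the control product into the operating room" (Protocol 6.4.3.4), and Appendix N returns the unassigned product only at step 24. The treating physician's assessment determines the endpoint (SAP 4.4.2). Protocol 6.2.3 restricts the surgeon to the assigned hemostat for the evaluated site.

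The loss allowance in Protocol 6.6.5 and SAP 4.2.1.1 covers technical failures "or subjects not treated according to randomization assignment, resulting in a sample size of 162 per arm".

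**The concern.** Membership of the deciding comparison is settled after randomization by someone who knows the assignment. If a PerClot-assigned subject with a difficult site is treated with Arista, As Treated removes a likely failure from PerClot and adds one to control. Both shifts favour non-inferiority. As written, an ITT analysis that misses the margin cannot prevent a declared success, and PP does not isolate the switched subjects because it retains them.

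At stake is the 2.5% one-sided error rate of the only test that decides the trial.

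**Working it through.** **Inputs from the plan.** "One-sided alpha = 0.025"; "Minimum 80% power"; 90% expected success in both arms; 1:1 allocation; 154 evaluable and 162 planned per arm (SAP 4.2.1.1); upper bound that "is less than 0.10" (SAP 4.2.1); Farrington-Manning score test (SAP Appendix A).

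**1. The plan's own power.** Power = Φ{[δ − (pC − pT) − 1.960·SE0] / SE1}. The constrained null proportions are 0.8313 and 0.9313.

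- SE0 = √[(0.8313·0.1687 + 0.9313·0.0687)/154] = 0.03641
- SE1 = √(2·0.9·0.1/154) = 0.03419
- (0.10 − 1.960·0.03641)/0.03419 = 0.8375, and Φ(0.8375) = 0.7988

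This matches Appendix A (0.79885). The loss allowance is 162 − 154 = 8 per arm for all causes.

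**2. Switching model (assumed).** The true state is the margin: PerClot 80%, Arista 90%, 154 per arm. Of the PerClot-assigned subjects, k have hard sites and are given Arista. Hard-site success is hP with PerClot and hA with Arista. The remaining 154 − k PerClot subjects succeed at rate (0.80·154 − k·hP)/(154 − k). The documents give neither k nor the hard-site rates, so two pairs are used (40%/60% and 65%/80%), plus a non-selective case (80%/90%).

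Expected As Treated proportions at k = 8:

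- 40%/60%: PerClot (123.2 − 3.2)/146 = 82.2%; Arista (138.6 + 4.8)/162 = 88.5%; apparent difference 6.3 points against a true 10.
- 65%/80%: PerClot (123.2 − 5.2)/146 = 80.8%; Arista (138.6 + 6.4)/162 = 89.5%; apparent difference 8.7 points.
- 80%/90%: PerClot 80.0%; Arista (138.6 + 7.2)/162 = 90.0%; difference unchanged at 10 points.

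**3. False non-inferiority, simulated with the score test.** With no switches the rate is about 2.5% on either set.

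| Hard-site success (PerClot/Arista) | Switches | As Treated | ITT | Both required |
|---|---|---|---|---|
| 40%/60% | 3 | 5.0% | 3.0% | 2.8% |
| 40%/60% | 8 | 14% | 4.2% | 4.1% |
| 65%/80% | 3 | 3.2% | 2.9% | 2.4% |
| 65%/80% | 8 | 5.0% | 3.8% | 3.0% |
| 80%/90% (non-selective) | 3 | 2.4% | 2.7% | 2.1% |
| 80%/90% (non-selective) | 8 | 2.5% | 3.3% | 2.1% |

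With 5 switches, As Treated gives 7.8% at 40%/60% and 3.8% at 65%/80%. ITT rises throughout because switched subjects bring Arista outcomes into the PerClot arm.

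**4. Power when both must pass.** At a true 90%/90% with random crossover of 0, 1, 2 and 5% per arm, power is 80.9, 79.0, 78.1 and 76.4%.

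**The case against.** Protocol 6.2.3 forbids using the other product, so a switch is a departure and not a discretionary choice. Appendix N brings the assigned device to the sterile field after randomization; both products being in the room does not put both at hand. Bleeding flux is measured, capped and used for stratification before the envelope is opened, which limits how difficult a site can be. Assigned arm, device identifier and device masses are recorded, randomization is a listed deviation type, and source verification is 100%. A discordant ITT result would be reported. All of this stands and makes heavy selective switching less likely. None of it changes what the success rule accepts if switching occurs.

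The direction is also assumed. Selective moves from Arista to PerClot would make As Treated conservative (0.2% with 8 switches at 40%/60%), and four selective moves each way leave it at about 2.3%. As Treated also resists the dilution that crossover brings to an ITT non-inferiority comparison, which is a sound reason to keep it in the rule.

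Three stronger readings are tempting and are not supported:

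- **The plan expects 5% of subjects to be switched.** The allowance is an upper limit that pools contraindication, misdiagnosis and death before treatment with treatment not as assigned. Eight switches per arm is an extreme case.
- **A handful of switches would turn a clear ITT failure into success.** Illustrations of this kind need every switched site to fail on Arista as well. At an assumed 60% Arista success, five failures out of five have probability 0.4⁵, about 1%.
- **As Treated hides randomized subjects who were never treated.** They have no 7-minute outcome because time zero is application. An ITT requirement would not restore them, and the best- and worst-case analysis in SAP 4.8 already covers missing endpoints.

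**Conclusion.** The gap in the success rule is real: one analysis set decides, its arms follow the device received, the operator is unblinded, no as-randomized result must concur, and PP does not remove wrong-device subjects. The documents do not show that switching will happen or that it would favour PerClot.

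If difficult sites were moved selectively from PerClot to Arista, As Treated error at 80% against 90% with 154 per arm would rise from 2.5% to about 3-5% with 3 switches and 5-14% with 8. The range comes from the assumed hard-site success rates (65%/80% to 40%/60%). Without selection, As Treated holds at about 2.4% and ITT drifts to about 3.3% at 8 switches. Neither set is therefore safe alone. This is a worthwhile, inexpensive strengthening of the rule, and it should be made.

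**What to change.** In SAP 4.2.3 and 4.3 and Protocol 6.6.7 and 6.6.9, define success as the upper 97.5% bound below 0.10 in both (a) the ITT analysis by randomized arm, among subjects with a 7-minute outcome, and (b) the As Treated analysis. Add receipt of the non-assigned device to the major deviations that exclude a subject from PP.

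Requiring both cuts the harshest case above from 14% to about 4.1%, and gives about 2.1% under non-selective switching. It does not fully restore 2.5% under strong selection, so the corrected PP result remains useful support.

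The cost is wording; ITT is already to be computed and no new data are needed. If every subject receives the assigned device, the two analyses coincide and power is unchanged. At 1-2% random crossover per arm, power falls from 80.9% to 79.0% or 78.1%, a loss of about 2-3 points.
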